1.1.3 Nonclinical

1.1.3.1 Safety

In a nonclinical setting, single-dose toxicology studies of cannabidiol reveal a relatively safe toxicology profile except at very high doses of the drug substance. Repeated dose toxicology studies highlight a potential impact of cannabidiol on spermatogenesis, follicle-stimulating hormone (FSH) levels, and a subset of immune responses. Full detail of these results may be found in the IB¹ and selected data are summarized below.

- In a repeated-dose toxicity study, monkeys treated with oral cannabidiol (0, 30, 100, or 300 mg/kg/day), spermatogenesis was inhibited.³⁶ Another study reported abnormal sperm in animals exposed to cannabidiol and that paternal exposure to cannabidiol is associated with a lower impregnation rate, a 2.3-fold increase in fetal loss, and a 5.2-fold increase in postnatal loss.³⁷
- Levels of FSH increased approximately 70% to 100% in Rhesus monkeys dosed with 100 and 300 mg/kg/day of cannabidiol.³⁸
- Blood sampling following repeated daily injections of 5 mg/kg/day cannabidiol for 14 days in adult male Wistar rats showed decreased total leukocyte number and total numbers of T and B cells and T helper and T cytotoxic subsets.³⁹ This immunosuppressive effect did not affect the total numbers of natural killer (NK) and NK T cells that are responsible for the primary, nonspecific antiviral, and antitumor immune response. Mechanistically, 0.5 to 10 μ M of cannabidiol suppressed interleukin-2 (IL-2) and interferon (IFN)- γ messenger ribonucleic acid (mRNA) expression, proliferation, and cell surface expression of the IL-2 receptor α chain in murine splenocyte cell suspensions.
- Human peripheral lymphocytes cultured with 3.2×10^{-6} M cannabidiol for 72 hours did not induce chromosomal aberrations.⁴⁰ Similarly, treatment with 20 to 250 μ M cannabidiol did not induce unscheduled deoxyribonucleic acid (DNA) repair synthesis in cultured human fibroblasts.⁴¹ Cultured lymphocytes harvested from prior *cannabis* users receiving oral doses of 1200 mg/day of cannabidiol for 20 days did not show an increase in chromosomal aberrations or sister chromatid exchange.⁴²
- Intraperitoneal (IP) injection of 1 or 10 mg/kg/day into mice resulted in 2- to 6-fold increases in chromosomal and nuclear aberrations in bone marrow cells harvest from these mice.⁴³
 - Conversely, human peripheral lymphocytes cultured with 3.2×10^{-6} M cannabidiol for 72 hours did not induce chromosomal aberrations.⁴⁴

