1.4 Risk-Benefit Analysis

As discussed in Sections 1.1.3 and 1.1.4, numerous nonclinical and clinical studies have examined other formulations of cannabidiol. Several areas of potential concern have been identified with the use of cannabidiol, especially in nonclinical studies. These include:

- Competitive binding of CYP proteins (thus, an impact on drug metabolism in the liver). Cannabidiol is metabolized predominantly by CYP3A4 and CYP2C19, and may inhibit these 2 isoenzymes, as well as having small effects on CYP3A5, CYP1A1, and CYP2C9
- Abnormal spermatogenesis
- Abnormal induction of FSH in males
- Potential downregulation of immune responses involving the T, B, T-helper, and T cytotoxic subsets of leukocytes and/or those dependent on IL-2 or IFN- γ .

Based on recent studies of cannabinoid administration in humans, controlled cannabidiol may be safe in humans and animals. However, further studies are needed to investigate these reported effects.

The concomitant medication guidelines and safety monitoring (clinical laboratory, ECG, vital signs, and physical and neurological examination assessments) planned for this study (see Sections 4.9 and 6.1) are intended to minimize these potential safety risks. Levels of cannabidiol and its 7-hydroxy (OH) metabolite in the plasma will also be monitored (see Section 6.2).

Stopping criteria for individual subjects will dictate termination of subject participation should a safety issue arise (see Section 3.4.3).

This study will allow subjects who previously completed INS011-14-029 or participated in INS011-15-054 and completed Part A (visit 6) continued access. This is particularly important for those who received therapeutic benefit in terms of seizure control during the previous studies. As reviewed in Section 1.2, patients with treatment-resistant seizure disorders continue to experience a significant unmet medical need despite ongoing treatment with currently available medications and procedures. Devinsky et al.⁷⁷ recently noted that treatment-resistant seizure disorders are particularly good candidates for cannabidiol intervention.

From a therapeutic perspective, the risk of exacerbating a subject's epilepsy symptoms will be minimized by examining the investigational product in an adjunctive setting in combination with the subject's established AED(s) treatment regime. Alternations may be made to the subject's AED background medication(s) as discussed in Section 4.3.

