6.1.1.1 Monitoring of AEs Potentially Related to Drug Metabolism

Cannabidiol inhibits drug metabolism mediated by a subset of CYP proteins (see Section 1.1.2). Thus, the Investigator and study center staff should monitor subjects who are taking concomitant medications that are metabolized by CYP2C19, CYP2C9, or CYP1A1 or by p-glycoprotein with special care. Medication(s) that is/are inhibitor(s) or inducer(s) or sensitive substrates of CYP3A4 should be monitored with special care.

The CYP proteins noted above metabolize a selection of clinically important AEDs. As such, subjects should be monitored for AEs that may be related to a change in the metabolism of background AEDs. These may include:

- Increases in liver enzymes
- Increases in side effects associated with background AEDs
- Development of new side effects associated with background AEDs.

Similarly, several AEDs are known inducers of CYP3A4.²⁴ As such, their use may result in alterations in the level of the investigational product. Plasma levels of cannabidiol and 7-OH cannabidiol will be assessed as described in Section 6.2.

The Investigator may choose to assess plasma levels of background AEDs with which the subject is being treated should AEs arise that may be due to altered metabolism of these medications (see above). As noted in Section 4.3, decisions to alter background AED medications and dosing due to safety concerns will be considered on a case by case basis.

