6.1.4 Clinical Laboratory Evaluations

All clinical laboratory tests will be reviewed for results of potential clinical significance throughout the study. The Investigator will evaluate any change in laboratory values. If the Investigator determines a laboratory abnormality to be clinically significant, it is considered a laboratory AE; however, if the abnormal laboratory value is consistent with a current diagnosis, it may be documented accordingly.

The following laboratory tests will be assessed at the time points specified by Table 1.

- Hematology: complete blood count (CBC) with differential, including platelet count, neutrophils, lymphocytes, eosinophils, basophils, monocytes, hemoglobin, and hematocrit
- Serum chemistry: total protein, albumin, creatinine, blood urea nitrogen (BUN), uric acid, total bilirubin, direct bilirubin, alkaline phosphatase, FSH, AST, ALT, glucose, calcium, phosphorus, bicarbonate, chloride, sodium, and potassium
- Urinalysis: specific gravity, pH, color, and presence of white blood cells (WBCs), red blood cells (RBCs), and proteins
- β -hCG in urine (pregnancy test)

LFTs (e.g., albumin, direct and total bilirubin, AST, and ALT) will be closely monitored to identify any damage that could be induced by the investigational product.

Levels of FSH will be monitored as a potential surrogate outcome for gametocyte damage.

Laboratory values outside the reference limits suspected to be of any clinical significance will be repeated. Subjects in whom suspected clinical significance is confirmed will either not be included or if already enrolled will be followed until normalization or for as long as the Investigator considers necessary. Additional laboratory variables may be performed for safety reasons if judged appropriate by the Investigator. Further details are provided in the Laboratory Manual.

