17.1.1. ALL TEAEs

TEAEs will be summarized by presenting the number and percentage of subjects having any TEAE, having any TEAE in each SOC, and having each individual TEAE as reported by PT. Furthermore, summaries by severity and relationship to the study medication will be presented according to the definition below. The most frequent (at least 5%) TEAEs and drug related TEAEs will also be provided.

For each summary, TEAEs will be reported by age category.

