17.3.1. LABORATORY REFERENCE RANGES AND MARKEDLY ABNORMAL CRITERIA

Quantitative laboratory measurements will be compared with the relevant laboratory reference ranges in SI units and categorized as:

- Low: Below the lower limit of the laboratory reference range (LLN).
- Normal: Within the laboratory reference range (upper and lower limit included).
- High: Above the upper limit of the laboratory reference range (ULN).

Document: C:\Users\q832483\Documents\Insy CSR\Pending\Ready for QC\New folder\Statistical Analysis Plan.docx
Author: [REDACTED] Version Number: V1.0 Final
Version Date: 04APR2017

Template No: CS_TP_BS016 – Revision 3
Effective Date: 01May2012

Reference: CS_WI_BS005

STATISTICAL ANALYSIS PLAN: PROTOCOL INS011-14-030

Page 29 of 40

In addition to the high and low quantitative laboratory assignments (as identified by means of the laboratory reference ranges), markedly abnormal values for liver function tests (LFTs) will also be identified and summarized by time point and age category for:

- Alanine aminotransferase (ALT) level >3 times ULN
- Aspartate aminotransferase (AST) level >3 times ULN
- Total bilirubin in excess of >2 times ULN

Markedly abnormal values for LFTs observed at the Follow-up visit will also be summarized by CBD status.

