APPENDIX 2. ADVERSE EVENTS OF SPECIAL INTEREST PREFERRED TERMS

- Anemia;
- Diarrhea;
- Fatigue;
- Blood FSH decreased;
- Blood FSH increased;
- Weight decreased;
- Weight increased;
- Decreased appetite;
- Hypersomnia;
- Lethargy;
- Sedation;
- Seizure;
- Somnolence;
- Status epilepticus;
- Aggression;
- Agitation;
- Irritability;
- Acute respiratory failure;
- Dyspnea;
- Respiratory arrest.

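### The protocol names liver and immune effects as risks, but the SAP plans no pooled once-per-subject adverse-event count for either and sets no leukocyte laboratory criterion

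*Protocol*

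**What the plan says.** **The risks.** Protocol 1.1.3.1 opens its nonclinical safety summary with the toxicology findings: "Repeated dose toxicology studies highlight a potential impact of cannabidiol on spermatogenesis, follicle-stimulating hormone (FSH) levels, and a subset of immune responses". It goes on to report lower leukocyte, T-cell and B-cell numbers in rats after repeated injections. Section 1.4 carries this into the risk-benefit discussion: "Potential downregulation of immune responses involving the T, B, T-helper, and T cytotoxic subsets of leukocytes". On the liver, Section 1.1.2 describes raised injury markers in cultured rat hepatocytes. Section 6.1.1.1 names "Increases in liver enzymes" among the events to watch for. Section 6.1.4 says that liver function tests "will be closely monitored to identify any damage that could be induced by the investigational product".

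**The AESI list.** SAP Appendix 2 has 20 preferred terms. It includes "Blood FSH increased" and the matching decrease. Anemia is the only blood-cell term, and SAP 17.1.6 also gives it a separate listing of red-cell values over time. No term is hepatic, and none concerns leukocytes. SAP 17.1.6 tabulates AESIs by SOC and PT, then by relationship, and by maximum severity for related events.

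**The general outputs.** SAP 17.1.1 counts subjects overall, per SOC and per PT, with severity and relationship summaries. It then adds a shorter table: "The most frequent (at least 5%) TEAEs and drug related TEAEs will also be provided". SAP 17.3 gives descriptive statistics, normal-range shifts by time point and the proportion of subjects with laboratory abnormalities of interest. SAP 17.3.1 defines those abnormalities: "markedly abnormal values for liver function tests (LFTs) will also be identified and summarized", namely ALT and AST above 3 times ULN and total bilirubin above 2 times ULN. Appendix 3 includes white cells, neutrophils and lymphocytes, so the data are collected.

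**The concern.** Long-term safety is the primary objective in SAP 2.1. A reader of the report will want one number for each risk the protocol names: how many subjects had any such event. For liver and leukocyte events that number is not among the outputs described. The selection also looks uneven. FSH is taken up from the same sentence as the immune concern, and anemia, which Section 1.4 does not list, gets its own output. The SAP gives no reason for the choice. If related events are spread over several near-synonymous terms, small rows would have to be added by eye, and they cannot be added correctly without knowing which subjects overlap.

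**Working it through.** **Step 1: set each risk against the planned outputs (SAP text).**

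| Output | FSH | Liver | Leukocytes |
|---|---|---|---|
| AESI terms, Appendix 2 | 2 | 0 | 0 |
| Subject counts per SOC and PT, severity, relationship (17.1.1) | yes | yes | yes |
| Normal-range shifts by time point (17.3) | yes | yes | yes |
| Threshold in 17.3.1 | none | ALT, AST and bilirubin, each separately | none |
| Pooled once-per-subject AE count | none stated | none stated | none stated |

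**Step 2: what PT rows can and cannot show.** The plan has no figure to reproduce beyond its maximum size: 60 + 20 = 80 (Protocol 3.4 and 8.1), which agrees. The event counts below are assumptions.

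- Smallest count that reaches the 5% table: 0.05 × 80 = 4 subjects.
- Suppose three related PTs with 3 subjects each: 3/80 = 3.75%, so all three fall below the cut.
- If the same 3 subjects had all three terms, the pooled count is 3/80 = 3.8% (exact 95% CI 0.8% to 10.6%).
- If all the subjects differ, it is 3 × 3 = 9, and 9/80 = 11.3% (exact 95% CI 5.3% to 20.3%).

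The PT rows are identical in both cases.

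The range is similar if fewer subjects roll over. At N = 60 the cut is 0.05 × 60 = 3, so up to 2 subjects per term stay below it, and the pooled count runs from 2/60 (3.3%) to 6/60 (10.0%). At N = 40 the cut is 2, and the pooled count runs from 1/40 (2.5%) to 3/40 (7.5%).

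**Step 3: does the SOC row supply the pooled count?** Only if all related terms fall in one SOC and little else does. I assume that laboratory-type terms (an enzyme increased, a cell count decreased) and clinical-type terms code to different SOCs. This is general MedDRA structure and is not stated in the documents. Under that assumption no SOC row is a hepatic or cytopenia count.

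**Step 4: do the laboratory tables supply it?** For the liver, in part. The thresholds are applied to ALT, AST and bilirubin separately and summarized by time point. They do not capture a smaller rise that an investigator judges clinically significant and so reports as an AE under Protocol 6.1.4.

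For leukocytes there are only shifts by time point. If one subject is low at Week 24 and one is low at Week 36, the tables look the same whether that is one subject or two. Protocol 8.3.4.2 asks for shift tables with each subject counted once at the worst grade. SAP 17.3 writes its shifts by time point, and 17.3.2 drops toxicity grading. SAP 6.3 keeps unscheduled values out of by-visit summaries but admits them to worst-case values where needed, with the shift table as its example. Whether a once-per-subject leukocyte result survives is therefore unclear.

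**The case against.** Much of the case against stands.

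- A reader might infer that these risks have no subject-level count at all. The documents do not support that. SAP 17.1 and 17.1.1 count each subject once per SOC and per PT, and 17.1.1.1 and 17.1.1.2 add worst-case severity and relationship. SAP 17.3 gives proportions of subjects for the liver criteria.
- A reader might infer that the 5% cut hides events. It does not, because that table is additional to the full SOC and PT table, for which no threshold is stated.
- A reader might infer that leaving terms out of Appendix 2 causes the splitting. It does not. Listed AESIs are also tabulated by SOC and PT, so lethargy, sedation, somnolence and hypersomnia stay in separate rows. Adding terms without a grouping would change little.
- A reader might ask for an infections AESI. The SOC row for infections already gives that count.

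The hepatic half is the weaker one. Section 1.4 describes the liver concern as an effect on drug metabolism, and Section 6.1.1.1 ties enzyme rises to background antiepileptic drugs. Section 6.1.4 does speak of damage, but monitors it through the tests for which the SAP sets thresholds.

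Nothing in the documents requires AESIs to mirror nonclinical findings. The output templates mentioned in SAP Sections 8 and 17.1 are not available here, so the gap is one in the SAP text.

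What remains after all this is that no described output pools related terms by subject for either risk, and no leukocyte criterion exists.

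**Conclusion.** The point holds as a modest gap. Two risks that the protocol names have general coverage but no direct cumulative answer: no pooled once-per-subject AE count for hepatic events or leukocyte cytopenias, and no leukocyte criterion in SAP 17.3.1. The leukocyte half is the stronger.

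The size is illustrative only. With three terms of 3 subjects each at N = 80, the unknown pooled rate spans 3.8% to 11.3%. It would be tempting to quote 11.3% alone, but that assumes no subject has more than one of the terms, and the event counts themselves are assumed. The reasoning also rests on the MedDRA assumption in the working.

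No planned analysis is invalidated, since the SAP makes no inference. This is a cheap improvement to a descriptive safety report.

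**What to change.** - **Appendix 2 and 17.1.6:** add two predefined groups. Hepatic events: enzyme, bilirubin and hepatobiliary terms. Leukocyte cytopenias: leukopenia, lymphopenia, neutropenia and the matching decreased-count terms. Give each group a row for subjects with at least one event, by relationship and by maximum severity. Fix the term lists before database lock.
- **17.3.1:** add the proportion of subjects, each counted once, whose white cell, neutrophil or lymphocyte count is newly below the lower limit of normal at any on-treatment test, unscheduled tests included. Show it against both baselines of SAP 6.2, as 17.3 already does for laboratory results.
- Do not add a separate infections group.

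The cost is some SAP wording and a few extra tables from data already collected and coded, with no new visit, sample or test. The downside is that mild low counts from intercurrent childhood illness will be included. With no control arm, the new rows must be read as descriptive.

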1.1.3.2 Efficacy in Epilepsy Animal Models

Plant-derived cannabidiol shows antiepileptic,⁴⁷ antipsychotic, antidystonic, anti-emetic, and anti-inflammatory properties in animal models.⁴⁸ These models support exploring the use of cannabidiol for the treatment of epilepsy.⁴⁹

As an example, the anticonvulsant activity of oral cannabidiol was investigated in adult rat model of seizures (induced by maximal electroshock or audiogenic sources).⁵⁰ Cannabidiol was effective against maximal electroshock-induced seizures (median effective dose [ED₅₀] = 18 mg/kg), but only minimally effective against audiogenic-induced seizures (ED₅₀ \geq 75 mg/kg). The neurotoxicity median tolerated dose (TD₅₀) was >100 mg/kg. Cannabidiol co-administered with different antiseizure drugs (e.g., phenytoin or carbamazepine) increased or reduced their anticonvulsant activity, indicating that synergism or antagonism with cannabidiol was drug specific.

1.1.4 Clinical

Clinical data described in the following sections were collected following administration of various extracts of cannabidiol as oral solutions or solid formulations.

1.1.4.1 Pharmacokinetics

Oral doses of cannabidiol (10 mg/kg/day) once daily for 6 weeks in patients with Huntington's disease results in mean weekly plasma concentrations of 5.9 to 11.2 μ g/L.^{51,52} The mean t_{1/2} for cannabidiol is 24 and 31 hours when administered intravenously (IV) or inhaled, respectively, with a range of 18 to 33 hours.⁵³ Cannabidiol is cleared from plasma at rates between 960 and 1560 mL/min and the distribution volume is estimated to be approximately 30 L/kg.⁵³

1.1.4.2 Overview of Safety

Clinical studies in various human populations indicate that cannabidiol has a favorable side-effect profile. Doses as high as 1500 mg are well tolerated.⁵⁴ No significant reactions or serious adverse events (SAEs) have been reported across a wide range of dosages and in both

acute and chronic settings. Bergamaschi et al.¹⁷ recently reviewed the safety of cannabidiol in humans examined in 221 subjects across 21 studies. As detailed in the IB, no significant safety issues were reported.

Selected studies in which more detailed information regarding safety outcomes are reviewed in Section 1.1.4.2.1.

Regarding doses of cannabidiol that have been examined in other studies, daily doses of 200 to 300 mg cannabidiol (or potentially more) may be safe.^{2,58} Clinical evaluation and therapeutic ranges of cannabidiol doses have been reported to be between 10 and 1500 mg/day, with the majority of reports evaluating doses in the 300 to 600 mg/day cannabidiol range. Furthermore, between 300 and 1500 mg have been used in humans without toxicity or SAEs.^{51,55,56,57} Cannabidiol PK has not previously been studied in a pediatric population.

1.1.4.2.1 Selected Detailed Clinical Safety Data

The following specific examples detail selected studies of the safety of cannabidiol use in humans:

- Ten (10) mg/kg daily dosing of cannabidiol was evaluated in a study of 15 subjects diagnosed with Huntington's disease.⁵¹ Only 15 abnormal clinical laboratory values were associated with cannabidiol treatment; these were largely limited to 4 subjects and exhibited no obvious pattern. No significant or clinical differences in cannabidiol were observed in a *cannabis*-specific side-effect inventory.
- Chronic oral administration of 10 mg cannabidiol daily for 21 days does not induce any changes in neurological (including electroencephalogram [EEG]), clinical (including electrocardiogram [ECG]), psychiatric, blood, or urine examinations in both healthy volunteers and epileptic patients.²
- Oral administration of cannabidiol in healthy volunteers (3 mg/kg daily for 30 days) and in epileptic subjects (200 to 300 mg daily for 135 days) was well tolerated. No signs of toxicity or serious side-effects were detected on neurological and physical examinations, blood and urine analysis, ECG, or EEG.^{2,58}
- Administration of single and repeated doses of cannabidiol for up to 20 days at a dose of 1200 mg/day does not impact pulse rate and blood pressure in human subjects with previous experience to *cannabis* smoking.⁵⁹
- Three (3) subjects with treatment-resistant schizophrenia have been dosed with 40 to 1280 mg/day of cannabidiol for up to 4 weeks without reporting side-effects.⁶⁰

- Two (2) subjects diagnosed with bipolar affective disorder did not report adverse effects upon receiving 600 to 1200 mg/day of cannabidiol for up to 24 days.⁶¹

1.1.4.3 Efficacy in Human Epilepsy

While efficacy is not a primary endpoint for this study (see Section 2.0), several preliminary studies of cannabidiol report reductions in seizure activity for a significant subset of subjects.

Cannabidiol was examined as an adjunctive therapy in 15 subjects with secondary generalized epilepsy with temporal focus who were refractory to conventional treatment.^{2,3} The 8 subjects randomized to the active arm received 200 to 300 mg/day of cannabidiol or placebo for up to 4.5 months in addition to previously established antiepileptic drugs (AEDs).^{2,58} Subjects tolerated cannabidiol well, with no signs of toxicity or serious side-effects. Four (4) of the 8 subjects receiving cannabidiol remained almost free of convulsive crises throughout the study and 3 others experienced partial improvement. The clinical condition of 7 subjects receiving placebo remained unchanged and 1 subject improved.

Parents of children with treatment-resistant epilepsy have sought cannabidiol-enriched *cannabis* for treatment.⁴ In a survey, these parents reported dosages of cannabidiol ranging from <0.5 to 28.6 mg/kg/day, as per results from medical *cannabis* testing facilities. Sixteen (16; 84%) of the 19 parents eligible to respond to the survey reported a reduction in their child's seizure frequency while taking cannabidiol-enriched *cannabis*. Of these, 2 (11%) reported complete seizure-freedom, 8 (42%) reported >80% reduction in seizure frequency, and 6 (32%) reported a 25% to 60% seizure reduction. Reported side-effects included fatigue and somnolence.

Realm Oil is an extract from a strain of *cannabis* known as Charlotte's Web and contains a cannabidiol:Δ⁹-THC ratio >20:1. Gedde and Maa⁵ reported on a small group of pediatric subjects diagnosed with various types of epilepsy who took Realm Oil for ≥3 months. Baseline seizure frequency for these subjects ranged from 5 to 2800 events per week. Eight (8; 73%) of these subjects reported a 95% to 100% reduction in seizure occurrence, 1 (9%) reported 75% reduction, and 2 (18%) reported 20% to 45% reduction.

